7.2.10 Safety Variables – Adverse Events

AE data are collected on the 'Adverse Events' eCRF page. The AE Description (Investigator term) will be analyzed on PT and SOC level using MedDRA.

Based on the information provided on the 'Adverse Events' eCRF page, the following definitions will be utilized:

- An ocular event will be identified, if the question 'Is this an ocular event?' is answered 'Yes'.
- An AE with missing severity will be counted as severe.
- A Serious Adverse Event (SAE) is any adverse event where the question 'Is the event serious?' has been answered as 'Yes'. If this question is not answered the event will be considered as 'Serious' for analysis purposes.
- *The following adverse events are considered to be of special interest (AESI) and by default shall be reported as SAEs (medically important criteria):*

- *Adverse Events that cause an unexpectedly severe progression of optic neuropathy as measured by central vision loss (i.e. decrease in visual acuity of >30 ETDRS letters or > +0.6 LogMAR lasting >1 hour compared with the last assessment of visual acuity at the last visit), by visual field testing, or by examination of the optic nerve.*
- *Adverse Events that cause a decrease in visual acuity to the level of Light Perception or worse lasting >1 hour.*
- *Adverse Events that require surgical intervention (e.g., conventional surgery, vitreous tap or biopsy with intravitreal injection of anti-infectives, or laser or retinal cryopexy with gas) to prevent permanent loss of sight.*
- *Adverse Events associated with severe intraocular inflammation (i.e., 4+ anterior chamber cell/flare or 4+ vitritis).*
- *Adverse Events that, in the opinion of the investigator, may require medical intervention to prevent permanent loss of sight.*

For analysis purposes, AESI will be identified by ticked box 'Medically significant or important medical condition' in the eCRF section 'SAE criteria'. This means in particular, that all AESIs will be considered as SAEs.

- An AE leading to premature withdrawal of the study treatment is defined as an AE where in the eCRF section 'Action taken with study treatment' the boxes 'Withdrawn' and 'Permanently' are ticked.
- An AE leading to study treatment interruption is defined as an AE where in the eCRF section 'Action taken with study treatment' the boxes 'Withdrawn' and 'Temporarily' are ticked.
- An AE leading to study discontinuation is defined as an AE where in the eCRF section 'Action regarding Patient' the box 'Patient Withdrawn' is ticked (this should match with the primary reason for early withdrawal of 'Adverse Event' on the End of Study eCRF page).
- An AE is classified as 'Related' to Study Treatment if the relationship to study medication recorded as 'Possible' or 'Probable' or 'Highly Probable'. An AE will be classified as unrelated to study medication if the relationship to study medication was recorded as 'None' or 'Unlikely'. AEs with missing relationship to study treatment will be counted as 'Related' to Study Treatment.
- A Fatal AE is defined as an AE where the outcome is recorded as 'Fatal'.

These definitions will apply accordingly also for the subsequent sub-classes of AEs.

Non Treatment-emergent adverse events (Non-TEAEs)

A Non-TEAE is defined as any AE, which started before the first administration of study treatment. An AE is considered as Non-TEAE, if the eCRF question 'Did the event occur:' was answered with 'Before Treatment Period'.

Treatment-emergent adverse events (TEAEs)

A treatment-emergent adverse event is defined as an AE that started on or after the date of the First Study Treatment Administration. An AE is considered as TEAE, if the eCRF question 'Did the event occurred:' was answered either with 'During Treatment Period' or 'During Follow-Up Period'.

TEAEs in Treatment Period

This is defined as a TEAE (as defined above) that started on or after the date of the First Study Treatment Administration but on or before the Week 8 Study Visit. A TEAE in

Treatment Period will be identified, if the eCRF question ‘Did the event occurred:’ was answered with ‘During Treatment Period’.

TEAEs in Follow-Up Period

This is defined as an TEAE with a start date after the Week 8 Visit. An TEAE will be considered as TEAE in Follow-Up Period, if eCRF question ‘Did the event occur:’ was answered with ‘During Follow-Up Period’.

For listing purposes, treatment day of onset of AE will be derived according to the definition given in section 7.1.

Missing Codes or Incomplete AE start dates:

In the event that coding information will not be available for a specific AE, the event will be presented as ‘Uncoded Event’. However, for final TLFs it is anticipated that all events are coded.

If the eCRF question ‘Did the event occur:’ was not answered, AEs will be classified to subclass Non-TEAE, TEAE in Treatment Period or In Follow-Up Period based on the AE onset date utilizing the definitions given above. If this is not possible, the event will be classified as TEAE in Treatment Period.

Missing and/or incomplete AE onset dates will be imputed for calculating relative start and stop days only. Dates will be listed as missing/incomplete [with “-“ replacing missing information] but the onset Day listed between square brackets to denote it was calculated based on missing data (i.e. [1]).

Missing and/or incomplete dates will be imputed in a manner that assumes the worst case scenario:

- For a missing start day (but month and year is available), onset is assumed on the first day of the respective month.
- For a missing start month (but year is available), onset is assumed on 1st January of the respective year.
- For a completely missing start date, no imputation will be performed.

If for Non-TEAEs this procedure results in an onset date before date of informed consent, informed consent date will be used.

If for TEAEs in the Treatment Period this procedure results in an onset date before date of first study treatment, date of first study treatment will be used.

If for TEAEs in the Follow-Up Period this procedure results in an onset date before date of Week 8 visit, date of Week 8 visit will be used.

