12.1.3. Serious Adverse Events

A serious adverse event (SAE) is defined as any adverse experience that, in view of either the Investigator or Sponsor, meets any of the following criteria:

- Results in death.
- Is life-threatening.

NOTE: Life-threatening means that the patient was at immediate risk of death from the reaction as it occurred, i.e., it does not include an event which hypothetically might have caused death had it occurred in a more severe form.

- Requires inpatient hospitalization or prolongation of existing hospitalization.

NOTE: In general, hospitalization means that the individual remained at the hospital or emergency ward for observation and/or treatment (usually involving an overnight stay) that would not have been appropriate in the physician's office or an out-patient setting. Complications that occur during hospitalization are AEs. If a complication prolongs hospitalization or fulfills any other serious criteria, the event is serious. When in doubt as to whether “hospitalization” occurred, the event should be considered serious.

- Results in persistent or significant disability/incapacity or a substantial disruption of a person's ability to conduct normal life functions.

NOTE: This definition is not intended to include experiences of relatively minor medical significance such as uncomplicated headache, nausea, vomiting, diarrhea, influenza, or accidental trauma (e.g., sprained ankle) which may interfere or prevent everyday life functions, but do not constitute a substantial disruption.

- Is a congenital anomaly/birth defect.
- Is an important medical event. *An important medical event is an event that may not result in death, be life-threatening, or require hospitalization but may be considered a SAE when, based upon appropriate medical judgment, it may jeopardize the patient and may require medical or surgical intervention to prevent one of the outcomes listed above. Examples of such medical events include allergic bronchospasm requiring intensive treatment in an emergency room or at home, blood dyscrasias or convulsions that do not result in patient hospitalization, or the development of drug dependency or drug abuse.*

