12.1.6. Adverse Events of Special Interest (Sight-threatening Events)

The following adverse events are considered to be of special interest and by default are to be reported as SAEs (medically important criteria):

- Adverse Events that cause an unexpectedly severe progression of optic neuropathy as measured by central vision loss (i.e. decrease in visual acuity of >30 ETDRS letters or > +0.6 LogMAR lasting >1 hour compared with the last assessment of visual acuity at the last visit), by visual field testing, or by examination of the optic nerve.
- Adverse Events that cause a decrease in visual acuity to the level of Light Perception or worse lasting >1 hour.
- Adverse Events that require surgical intervention (e.g., conventional surgery, vitreous tap or biopsy with intravitreal injection of anti-infectives, or laser or retinal cryopexy with gas) to prevent permanent loss of sight.
- Adverse Events associated with severe intraocular inflammation (i.e., 4+ anterior chamber cell/flare or 4+ vitritis).
- Adverse Events that, in the opinion of the investigator, may require medical intervention to prevent permanent loss of sight.

During the study all sight threatening events will be considered equivalent to a SAE and will be reported following the procedures described below for the reporting of a SAE.

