7.2.7 Primary Safety Outcomes

The primary safety outcomes of the study are:

Unexpected severe progression of optic neuropathy (USPON)

Unexpected Severe Progression of Optic Neuropathy will be measured a) by a central vision loss; b) by visual field testing; and/or c) by examination of the optic nerve. It is recorded per eye on the Follow-Up Visits of the eCRF pages 'Best Corrected Distance Visual Acuity', 'Humphrey Visual Field Monitoring', 'Electroretinography' and Ocular coherence tomography' via a tick box 'Was an unexpected severe progression measured...' (Yes/No).

USPON will be investigated only for treated eyes, i.e. if an eye is not treated, the respective tick box will not be considered for definition of primary outcome.

[figure not shown]
For a patient, USPON occurred, if in any of the following assessments the respective question on unexpected severe progression is answered 'Yes':

- a) from BCDVA assessments: eCRF question is ticked 'Yes' for at least one treated eye at any Follow-Up Visit after first study treatment administration (including unscheduled visits).
- b) from HVF assessments: eCRF questions is ticked 'YES' for at least one treated eye in at least one assessment during Treatment or Follow-Up Period (i.e. performed after first study treatment administration). An assessment is considered as performed during Follow-Up Period, if Test Date and Test time as documented on eCRF Page 'Humphrey Visual Field Monitoring' was after Week 8 Visit (See also Section 7.2.9 for Details).
- c) from ERG assessments: eCRF question is ticked 'Yes' for at least one treated eye at any Follow-Up Visit after first study treatment administration (including unscheduled visits).
- d) from OCT assessments: eCRF question is ticked 'Yes' for at least one treated eye at any Follow-Up Visit after first study treatment administration (including unscheduled visits).

As supportive variable, the occurrence of USPON during Treatment Period will be derived, which is defined as an USPON, which was recorded between the first study treatment administration and Week 8 Visit/Study termination Visit (for patient withdrawn during the treatment period).

Intolerance or allergy to the drug

The occurrence of intolerance and allergy to the drug will be identified during the BDRM by reviewing reported Preferred Terms of Treatment Emergent Adverse Events (for definition see Section: 7.2.10).

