Adverse events affecting ocular function or eye pressure, which differ from those expected in the course of glaucoma, which are thought to be potentially related to the drug (Unexpected Related AEs affecting ocular function/eye pressure)

The occurrence of these events will be identified via the respective question on the AE form. It is expected, that only adverse events, which are occurring during treatment period, will be flagged for this endpoint by the investigator. So, no separate analysis is foreseen by study period.

Local or systemic toxicities considered serious adverse events that are potentially related to the drug

The occurrence of local and systemic toxicities will be identified via the respective question on the AE form. It is expected, that only adverse events, which are occurring during treatment period, will be flagged for this endpoint by the investigator. So, no separate analysis is foreseen by study period.

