10.8 Adverse Events and Further Safety Assessments

10.8.1 Adverse Events

10.8.1.1 Brief Summary of Adverse Events

An overview summary will be provided for the SAF by presenting of events as well as number and percentages of affected patients for AEs, TEAEs, TEAEs in the Treatment Period, TEAEs in the Follow-Up Period, TEAEs leading to Premature Withdrawal of Study Treatment, TEAEs leading to Study Discontinuation, Treatment Related TEAEs, Serious AEs, Serious TEAEs, Treatment Related Serious TEAEs Fatal AEs, AESIs, TEAEs by severity, TEAEs in the Treatment Period by severity, TEAEs in the Follow-Up Period by severity, TEAEs by age category, TEAEs in the Treatment Period by age category, TEAEs in the Follow-Up Period by age category.

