Table 14.2-3.1	Summary of BCDVA Scores	ITT	U	Y
Table 14.2-3.2	Summary of Changes from Baseline in BCDVA Scores	ITT	U	Y
Table 14.2-3.3	Analysis of Changes from Baseline in BCDVA Scores	ITT	U	N
Table 14.2-4.1	Summary of LogMAR	ITT	U	Y
Table 14.2-4.2	Summary of Changes from Baseline in LogMAR	ITT	U	Y
Table 14.2-4.3	Analysis of Changes from Baseline in LogMAR	ITT	U	N
Table 14.2-5.1	Summary of PhNR	ITT	U	Y
Table 14.2-5.2	Summary of Changes from Baseline in PhNR	ITT	U	Y
Table 14.2-5.3	Analysis of Changes from Baseline in PhNR	ITT	U	N

TLF number	Title	Analysis Set	U/R	SR
Table 14.2-6.1	Summary of RNFL Variables	ITT	U	Y
Table 14.2-6.2	Summary of Changes from Baseline in RNFL Variables	ITT	U	Y
Table 14.2-6.3	Analysis of Changes from Baseline in RNFL Variables	ITT	U	N
Table 14.2-7.1	Summary of PanoMap Variables	ITT	U	Y
Table 14.2-7.2	Summary of Changes from Baseline in PanoMap Variables	ITT	U	Y
Table 14.2-7.3	Analysis of Changes from Baseline in PanoMap Variables	ITT	U	N
Table 14.2-8.1	Summary of Ganglion Cell Variables	ITT	U	Y
Table 14.2-8.2	Summary of Changes from Baseline in Ganglion Cell Variables	ITT	U	Y
Table 14.2-8.3	Analysis of Changes from Baseline in Ganglion Cell Variables	ITT	U	N
Table 14.3.1-01.1	Overall Summary of Adverse Events	SAF	U	Y
Table 14.3.1-02.1	Summary of Adverse Events by System Organ Class and Preferred Term	SAF	U	Y
Table 14.3.1-03.1	Summary of TEAEs by System Organ Class and Preferred Term	SAF	R	Y
Table 14.3.1-04.1	Summary of Treatment Related TEAEs by System Organ Class and Preferred Term	SAF	R	Y
Table 14.3.1-05.1	Summary of TEAEs leading to Premature Withdrawal of Study Treatment by System Organ Class and Preferred Term	SAF	R	Y
Table 14.3.1-06.1	Summary of TEAEs leading to Study Discontinuation by System Organ Class and Preferred Term	SAF	R	Y
Table 14.3.1-07.1	Summary of Serious TEAEs by System Organ Class and Preferred Term	SAF	R	Y
Table 14.3.1-08.1	Summary of TEAEs by Severity, System Organ Class and Preferred Term	SAF	U	Y
Table 14.3.1-09.1	Summary of TEAEs by Age Category, System Organ Class and Preferred Term	SAF	U	Y
Table 14.3.1-10.1	Summary of TEAEs in the Treatment Period by System Organ Class and Preferred Term	SAF	R	N
Table 14.3.1-11.1	Summary of TEAEs in the Treatment Period by Severity, System Organ Class and Preferred Term	SAF	R	N
Table 14.3.1-12.1	Summary of TEAEs in the Treatment Period by Age Category, System Organ Class and Preferred Term	SAF	R	N

TLF number	Title	Analysis Set	U/R	SR

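### SAP 7.2.10 identifies adverse events of special interest only by a generic seriousness box, so the count can include events that do not threaten sight and miss qualifying events without the tick

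*SAP*

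**What the plan says.** Protocol 12.1.6, which carries sight-threatening events in its title, introduces five criteria with "The following adverse events are considered to be of special interest and by default are to be reported as SAEs (medically important criteria". In short, these are unexpectedly severe optic nerve progression, a fall in acuity to light perception or worse lasting over an hour, surgery needed to save sight, severe intraocular inflammation, and the investigator's opinion that medical treatment may be needed to save sight. The definition is of adverse events. Seriousness follows from meeting a criterion.

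Protocol 12.1.3 defines the important medical event as one of the general grounds for calling any event serious. Its examples include "allergic bronchospasm requiring intensive treatment in an emergency room or at home, blood dyscrasias or convulsions".

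SAP 7.2.10 reproduces the five criteria and then gives the rule for analysis: "For analysis purposes, AESI will be identified by ticked box", followed by the name of the medically significant box in the SAE section of the adverse event form. No second condition is attached. The same list of definitions uses another question from that form ("An ocular event will be identified, if the question"), but the AESI rule does not draw on it.

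SAP 10.8.1.1 puts AESIs in the overview summary, in the run "Treatment Related Serious TEAEs Fatal AEs, AESIs, TEAEs by severity". SAP section 12 marks that table, "Overall Summary of Adverse Events", for repetition at the final analysis.

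**The concern.** The protocol supports one direction of inference: an event that meets an AESI criterion should have the box ticked. The SAP uses the reverse: an event with the box ticked is an AESI. The box belongs to a general seriousness criterion, so the reverse does not follow.

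The line labelled AESI could therefore report a sight-threatening event where there was none. Safety is the primary objective of this trial, and true events in this category may be few or absent, so a single non-ocular SAE could change what the line appears to say. The same rule leaves out a qualifying event whose box was not ticked, for example one recorded as serious only because of hospitalisation, or one recorded as non-serious.

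The SAP's own note on visual acuity in 7.2.9 describes AESIs in terms of substantial change since the last visit. Its authors thus had a vision-related concept in mind, which the derivation rule does not enforce.

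**Working it through.** The plan has no figure to reproduce. The check is to apply the SAP rule and the protocol definition to the same event.

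| Event | Meets a Protocol 12.1.6 criterion? | Box ticked? | AESI by protocol | AESI by SAP 7.2.10 |
|---|---|---|---|---|
| Qualifying event, reported as instructed | Yes | Yes | Yes | Yes |
| Convulsion without hospitalisation, serious as an important medical event | No | Yes | No | **Yes** |
| Qualifying event without the tick (only another seriousness ground marked, or recorded as non-serious) | Yes | No | Yes | **No** |
| Any other event | No | No | No | No |

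The second row follows from Protocol 12.1.3, which gives convulsions without hospitalisation as an example of this seriousness ground. The third row requires a departure from the protocol's default reporting instruction.

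**Does anything else narrow the rule?** SAP 7.2.7 is more specific for the primary safety outcomes that rest on adverse events. For intolerance or allergy, "The occurrence of intolerance and allergy to the drug will be identified during the BDRM by reviewing reported Preferred Terms". For unexpected related events affecting ocular function or eye pressure, "The occurrence of these events will be identified via the respective question on the AE form", and related serious toxicities are handled in the same way. Neither document describes a matching question or review step for AESIs. SAP 10.8.1.2 has no AESI table and 10.8.1.3 no AESI listing.

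**Size of one error.** Inputs: 60 patients randomised 40:20 (Protocol synopsis), and the assumption that all are dosed, so that the Safety Set is 40 and 20.

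- rhNGF: 1/40 = 2.5%
- Vehicle: 1/20 = 5.0%
- Overall: 1/60 = 1.7%

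These are the steps that any one-patient change makes in any row of the table. They show scale only and do not estimate how often the error would occur.

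**The case against.** The strongest case on the other side is that very little depends on this rule. It feeds one descriptive line. A non-ocular event counted there would still appear by system organ class and preferred term among the serious TEAEs, if treatment-emergent, and in the listing of serious AEs. In 60 patients a reader could probably reconcile the line. An over-inclusive flag also fits the SAP's habits: 7.2.10 counts missing severity as severe, missing seriousness as serious and missing relationship as related. A box ticked by the investigator is simple and needs no judgement after unmasking. All of this stands, and it keeps the point minor. It does not make the label correct, and the SAP does not give conservatism as its reason for the rule.

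A reader might infer more than the documents support:

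- *That the primary safety result is affected.* It is not. Under SAP 7.2.7, severe progression comes from tick boxes on the acuity, visual field, ERG and OCT pages. The other outcomes come from preferred-term review or their own form questions.
- *That the rule hides sight-threatening events.* If the default reporting instruction is followed, every qualifying event has the box ticked and the error is an over-count only.
- *That misclassified events would go unreviewed.* SAP 8.4.3 leaves the scope of data review to a separate plan, and 5.1 refers to data management documents. None of these is available here, so the statement that nothing corrects the rule covers the protocol and SAP only.
- *That misclassification is likely.* The documents give no rate for box-ticked SAEs that fall outside the criteria.

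**Conclusion.** The point holds as a minor error in a derivation rule. As written, SAP 7.2.10 treats a reporting consequence of an AESI as enough to identify one. Followed exactly, it can over-count AESIs, and it can under-count them where the default reporting instruction was not followed. The consequence is confined to the AESI line of the overview table, at both the main and the final analysis. If all 60 patients are dosed 40:20, each misclassified patient shifts that line by 2.5 points on rhNGF, 5.0 on vehicle and 1.7 overall. The error arises only if such an event occurs, and its frequency cannot be estimated from the documents. The counts of SAEs and the primary safety outcomes do not depend on how AESIs are identified.

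**What to change.** In SAP 7.2.10, define an AESI as any adverse event, not only an SAE, that meets at least one of the five Protocol 12.1.6 criteria. Use the box to find candidates and not to decide.

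- **Before unmasking.** At the blind data review, check all SAEs, whichever seriousness box is ticked, and all AEs with the ocular-event question answered yes. The review of intolerance or allergy is only a partial precedent, because preferred terms cannot settle letters lost, duration, inflammation grade or investigator opinion. Use SAE narratives, the BCDVA data and investigator queries for these. Query any qualifying event recorded as non-serious.
- **Later events.** SAP 8.4.3 limits the blind review to AE data documented up to the soft lock. Apply the same written criteria to later events at the reduced data review, and label them as classified after unmasking.
- **Reporting.** Flag AESIs in the existing adverse event listing.

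If the sponsor prefers to keep the box rule, the least change is to label the row as medically important SAEs and not as AESIs.

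The cost is SAP wording, one flag in an existing listing, and a small amount of work at two reviews already planned. The drawback is that some late events would be classified after unmasking, which the box rule avoids. An event recorded as non-serious and not flagged as ocular would still escape the check.

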2. STUDY PLAN

| SCHEDULED VISIT WEEK | Baseline Visit (Screening) ¹ | Day 0 Therapy Initiation | Week 1 (± 2 days) | Week 4 (± 4 days) | Week 8 (± 7 days) | Week 12 (± 7 days) | Week 32 (± 7 days) |
|---|---|--------------------------|-------------------|-------------------|-------------------|--------------------|--------------------|
| GENERAL ASSESSMENTS | | | | | | | |
| Informed consent | X | | | | | | |
| Randomization | | X | | | | | |
| Inclusion / Exclusion criteria | X | X | | | | | |
| Pregnancy test (if applicable) | | X | | | X | | |
| Demographics, Medical History, Medications ² | X | X | X | X | X | X | X |
| AE assessment | X | X | X | X | X | X | X |
| VISUAL SYSTEM EXAMS | | | | | | | |
| Best Corrected Distance Visual Acuity (BCDVA) | X | X | | | X | X | X |
| IntraOcular Pressure (IOP) ³ | X | X | X | X | X | X | X |
| Slit lamp examination (SLE) | X | X | X | X | X | X | X |
| External ocular examination | X | X | X | X | X | X | X |
| Humphrey 24-2 or 10-2 Visual Field ⁴ | X ⁵ | X | X ⁶ | | X ⁷ | | |
| Dilated Fundus Ophthalmoscopy | X | X | | | X | X | X |
| OCT (retinal thickness) | | X | | | X | X | X |
| Mitochondrial redox potential | | X | | X | X | X | X |
| Full field and pattern ERG ⁸ | | X | | | X | X | X |
| STUDY THERAPY | | | | | | | |
| Visual Analogue Scale (VAS) for ocular tolerability | | X | X | X | X | X | |
| Study drug dispensing ⁹ | | X | | X | | | |
| Assess medication dosing compliance ¹⁰ | | | | X | X | | |

¹ Baseline Screening Visit will occur within 4 weeks prior to initiating therapy.

² Demographic information to be collected only at screening visit including medications taken within the preceding 30 days.

³ IOP testing will be performed using Goldmann Tonometer.

⁴ Visual Field testing will be performed using Sita Standard.

⁵ 2 fields on different days for a total of 3 before initiating treatment.

⁶ 3 fields within 4 weeks until the end of treatment.

⁷ 3 fields within 4 weeks until the end of follow-up.

⁸ Full-field performed once at Therapy Initiation (Day 0) visit, at Week 8, at Week 12 and at Week 32.

⁹ At Day 0 instruct the patient to self-administer drug at home and return to next planned visit.

¹⁰ At Week 4 and 8 patient will be instructed to return all used and unused IP and the freezer bag.

Table Note: Required procedures for a scheduled visit may be performed over 2 consecutive days.

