8.1.2. Other medications

Upon enrolment, the previous topical glaucoma medications of patients will be continued normally, however, it will be required that previous topical ophthalmic medications used for intraocular pressure control will not be changed during the course of the study. Any other topical ocular treatment not related to intraocular pressure control for glaucoma, that is used before enrollment, will need to be discontinued and patients will only be allowed to use the study medication provided by Dompé and preservative-free artificial tears during the course of randomized controlled treatment period.

No rescue medication is planned for this study.

8.2. 24 WEEK FOLLOW-UP PERIOD

At the conclusion of the controlled treatment period at Week 8, patients will be discontinued from study treatment. During the 24 week follow-up period (Weeks 9-32) the patients will be followed without any protocol required study medication, however, preservative-free artificial tears (not provided by Dompé) may be prescribed as needed as at the discretion of the study investigator.

The first 4 weeks of the follow up period will be referred to as masked follow-up (and patients treatment will be kept masked) while the following 20 weeks will be referred to as unmasked follow-up (patients treatment will be unmasked at week 12) and the database will be locked. The database will be locked and the study will be complete after the last randomized patient has completed 4 weeks of the follow up period (Week 12 Visit). However, after the database lock patients still in the follow up period will continue with scheduled visits for the remainder of the 24 week follow up period.

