12.3. RECORDING

Adverse Events: all AEs (non-serious and serious) which occur during the course of the study will be recorded in the eCRF. Any pre-existing medical conditions or signs/symptoms present in a patient prior to the start of the study (i.e., before informed consent is signed), should be entered in the baseline history section of the eCRF of the EDC system. Subsequent to signing an informed consent form, all untoward medical occurrences that occur during the course of the study must be documented on an Adverse Event Form (AEF) in the eCRF of the EDC system. A separate AEF must be filled out for each event. When possible, signs and symptoms indicating a common underlying pathology should be documented as one comprehensive event. For each recorded event, the AE documentation must include the onset date, outcome, resolution date (if event is resolved), intensity (i.e., severity), any action with study treatment taken as a result of the event, and an assessment of the adverse event relationship to the study treatment.

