12.3.2. Severity of AEs

The Investigator will grade the severity of any AE using the definitions in the Table below. For each episode, the highest severity grade attained should be reported.

Severity of the Adverse Event

| | |
|----------|--|
| Mild | Grade 1 - Does not interfere with patient's usual function (awareness of symptoms or signs, but easily tolerated [acceptable]). |
| Moderate | Grade 2 - Interferes to some extent with patient's usual function (enough discomfort to interfere with usual activity [disturbing]). |
| Severe | Grade 3 - Interferes significantly with patient's usual function (incapacity to work or to do usual activities [unacceptable]) |

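### The SAP's treatment-emergent definition has no worsening clause, so an adverse event that opens in screening and worsens on drug can be left out of the TEAE tables if the site keeps it as one record

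*SAP*

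**What the plan says.** SAP 7.2.10 gives two mirror-image definitions: "A treatment-emergent adverse event is defined as an AE that started on or after the date of the First Study Treatment Administration" and "A Non-TEAE is defined as any AE, which started before the first administration of study treatment". Neither mentions an increase in severity or a change to serious after dosing.

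The class is read first from an eCRF question on whether the event occurred before treatment, during treatment or during follow-up. Only if that question is blank does the date decide: "AEs will be classified to subclass Non-TEAE, TEAE in Treatment Period or In Follow-Up Period based on the AE onset date".

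Three recording rules in the protocol feed this classification:

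- Collection starts at consent (12.3): "Subsequent to signing an informed consent form, all untoward medical occurrences that occur during the course of the study must be documented". The schedule (section 2) adds: "Baseline Screening Visit will occur within 4 weeks prior to initiating therapy".
- Each event has one form (12.3): "A separate AEF must be filled out for each event".
- Each episode has one grade (12.3.2): "For each episode, the highest severity grade attained should be reported".

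No passage says whether the worsening of an adverse event that is already open starts a new record.

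**The concern.** Safety and tolerability against vehicle is the primary objective, and the primary safety outcomes are described without formal inference. A reader will therefore judge safety largely from counts in the treatment-emergent tables, in arms of 40 and 20. A drug can cause harm by aggravating a symptom that is already present. A definition that looks only at when the event began cannot see that kind of harm, and the highest-grade rule can attach a grade reached on drug to a record labelled as pre-treatment.

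The gap runs against the SAP's own cautious habits in the same section. There, a missing severity counts as severe, a missing causality as related, and an event that cannot be placed in time as treatment-emergent in the treatment period.

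**Working it through.** The plan states no figure on this point and made no formal sample-size calculation, so there is nothing to reproduce. The check is a trace through the rules, followed by an estimate of scale.

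**Trace.** Take an ocular event that starts mild between consent and first dose, becomes severe on study drug and is rated related.

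*Route A: the site keeps one record.*

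1. Onset is before first dose and the eCRF period answer is before treatment, so SAP 7.2.10 makes it a Non-TEAE.
2. Protocol 12.3.2 sets its grade to severe.
3. It is absent from Tables 14.3.1-03.1 to 14.3.1-15.1. These cover all TEAEs, related TEAEs, TEAEs leading to treatment withdrawal or study discontinuation, serious TEAEs, and the splits by severity, age and period. SAP 10.8.1.2 plans no severity or relatedness table for adverse events as a whole.
4. It is outside the intolerance/allergy review, because SAP 7.2.7 bases that outcome on the preferred terms of TEAEs.
5. It remains in Table 14.3.1-02.1 (all adverse events, no severity split) and in the overview row for all adverse events, plus the serious and special-interest rows if it qualifies. It also remains in the adverse event and action-taken listings and, if serious, the serious adverse event listing. If the patient leaves the study because of it, it shows as a discontinuation reason in Table 14.1-1.2.

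*Route B: the site enters the worsening as a new adverse event.*

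1. Protocol 11.5.4 (clinically relevant change from baseline in an assessment) and 12.2 (clinically relevant change in a concomitant condition, study parameter or questionnaire response) permit this.
2. Onset is then on treatment, so the new record is a TEAE and is counted everywhere.

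Both routes are compatible with the text. The same clinical course is therefore counted or not counted according to how it was entered.

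**Which events are exposed.** Conditions present before consent go into baseline history (Protocol 12.3), so their worsening on drug would be a new adverse event and a TEAE. The gap is limited to adverse events that start between consent and first dose.

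**Effect of one patient.**

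- rhNGF: 1/40 = 2.5 percentage points.
- Vehicle: 1/20 = 5.0 percentage points.
- For one preferred term on rhNGF, the count changes from 0/40 (exact 95% interval 0 to 8.8%) to 1/40 (0.1 to 13.2%).

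**How many patients.** The documents give no rates. Assume that 5 to 20% of patients have a screening adverse event and that 10 to 30% of those worsen on treatment, equally in both arms.

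- Low end: p = 0.05 × 0.10 = 0.005. Expected patients = 60 × 0.005 = 0.3. Chance of at least one = 1 − 0.995^60 = 26%.
- High end: p = 0.20 × 0.30 = 0.06. Expected patients = 60 × 0.06 = 3.6. Chance of at least one = 1 − 0.94^60 = 98%.
- By arm: 40p = 0.2 to 2.4 on rhNGF and 20p = 0.1 to 1.2 on vehicle.

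**The case against.** The strongest reply is that nothing obliges the site to keep the worsening in the old record. The term episode is not defined, each event needs its own form, and Protocol 11.5.4 and 12.2 make a clinically relevant change an adverse event in its own right. The VAS covers burning/stinging, itching, ocular pain and photophobia, so aggravated ocular symptoms have a natural way into a new report. This stands in part: the loss is conditional. It does not close the gap, because neither section tells the site to open a new record for an adverse event that is already open.

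The second reply is that aggravation is measured elsewhere. This also stands. VAS change from baseline is tested at Weeks 1, 4 and 8, IOP change and slit-lamp shifts are tabulated, and unexpected severe progression of optic neuropathy has its own tick boxes. Two further primary safety outcomes come from adverse-event form questions with no treatment-emergent filter, although the SAP expects only treatment-period events to be flagged there.

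Three stronger readings are tempting but not supported:

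- *Such events always vanish from the safety output.* They do not. Route B counts them, and even under Route A the displays listed above retain them.
- *The trial itself provokes screening symptoms by stopping other eye drops.* Protocol 8.1.2 says "Any other topical ocular treatment not related to intraocular pressure control for glaucoma, that is used before enrollment, will need to be discontinued". However, it ties the restriction on permitted drops to the controlled treatment period, and SAP 3.3 usually starts dosing on the day after randomization. Symptoms from stopping could begin on or after first dose and count as TEAEs. The documents do not say that stopping causes irritation.
- *The comparison is biased toward no difference.* That holds only if rhNGF aggravates existing symptoms more than vehicle does, which the documents do not establish.

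**Conclusion.** The point holds in conditional form. As written, the rule can place an aggravation that occurred on drug outside every treatment-emergent table and outside one primary safety outcome, depending on how the site enters it. The size is probably small in patients: 0.3 to 3.6 of 60 under the assumed rates, which are illustrative and not taken from the documents. It is not negligible in this design, because one patient moves an arm's incidence by 2.5 or 5 points and the safety comparison is descriptive. The other displays limit the harm but do not replace the severity, relatedness and withdrawal tables that readers will use. The change is worth making before unmasking.

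**What to change.** 1. **SAP 7.2.10.** Define a TEAE as an adverse event that started, or that increased in severity or became serious, on or after first dose. Amend the Non-TEAE definition to match.
2. **eCRF completion guidance.** When an adverse event open at first dose worsens afterwards, enter the worsening as a new record with its own onset date and grade, and leave the earlier record at its pre-dose grade. The definition alone is not enough, because the eCRF period answer decides the class and does not capture worsening.
3. **Data already entered.** At the masked data review, before unmasking, query each Non-TEAE record that was ongoing at first dose and has a high grade, an action taken or a related rating. Obtain the date of worsening and record the resulting class in the review minutes.

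The cost is a short SAP revision, a line of guidance and a few queries. TEAE counts will rise slightly. In the all-adverse-event table the number of events also rises, but patients are counted once per term, so a patient coded to the same term is not counted twice. A protocol amendment is needed only if section 12.3 itself is edited.
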